8.5	Post-Treatment Efficacy Observations	60
8.6	Assignment of Doses to Adverse Events and Laboratory Assessments.....	60
8.7	Concomitant Medications	62
8.8	Counting Rules for Adverse Events	62
8.9	Fasting State.....	63
8.10	Percent Compliance Calculation	63
8.11	Strip Sign for Selected Laboratory Data.....	63
9	CONTENT OF REPORTS	63
10	CHANGES OF ANALYSIS FROM PROTOCOL.....	63
11	REFERENCES	64
12	SUMMARY OF CUTOFFS FOR ANALYSES WHICH EXCLUDE RESULTS AFTER TREATMENT DISCONTINUATION.....	65

AMENDMENT HISTORY

Date	Brief description of change
April 6, 2016	Initial Approved SAP
Version 2, September 27, 2017	
• Inserted texts from the core SAP and removed the references to core SAP.• Definition of confirmed hypoglycemia was updated.• Start of long-term treatment period was clarified in Section 6.1.• Section 6.3.5 was added to include the definition of Full Analysis Set. Following subsections were renumbered.• In Section 6.3.6 the definition of Evaluable Subjects Data Set was updated.• Section 7.1.9 for analysis of 6-point self-monitored blood glucose data was updated.• Table 7.2.1 for list of relevant protocol deviations and their exclusion level was updated.• Section 7.3.2 for demographics and baseline characteristics was updated.• In Section 7.4.1 additional categories were added for duration of exposure• Section 7.5.2 was updated by adding new sensitivity analyses for primary endpoint.• Section 0 was added for handling missing efficacy data which includes additional MI based sensitivity analysis. Following sections were renumbered.• Section 8.2 for selecting observations when there are multiple observations in a single visit window was updated.• Section 8.3 for laboratory evaluations was updated to include only data from central laboratory in safety tables• Section 8.4 was updated by adding visit windows for HbA1c and weight.• Section 10 was added to list the changes in analysis from protocol. Following section was renumbered.

Date	Brief description of change
Version 3, 1 October 2019	
During ST CSR appendices development, following discrepancies were identified in SAP:
 

• Section 7.6.1, 2nd paragraph: Reference to the section number of “Counting rules for AE”, updated to be Section 8.8
• Section 7.1.10, Figure 7.1.3-1 Reference#7 mentioned in the foot note of this figure has been updated to #3, as listed in section 11
• APPENDIX 2, Quality-of-Life Scaling Protocol number corrected from CV181-369 to CV181-365 
As per protocol version 5.0
 

• Sections 4.3 and 7.5.5.3 the time point for obtaining last MRI image is W156, the time point to be changed to W122 +/- 4 weeks 
As the ST+LT analysis was planned the following updates were made:
 

• Sections 2.7, 7.5.8, 7.6.5.4, 12 were added
• Clarification of, and details pertaining to, the ST analyses were added in order to reliably and robustly reproduce the results at the ST+LT timepoint, and for any future analysis. Confirmation was added throughout the document to identify which datasets and analyses were applicable to the short-term and/or short-term and long-term treatment periods. Section 7.1.2 – removed stratum from the model, and confirmed the interaction term Section 7.1.8 – removed integration of group's modelled probability of response over the observed distribution of baseline covariate Section 7.1.1.3, 7.5.3 and 7.6.6.2 – details of handling missing data were clarified Section 7.1.4 – updated the list of summary stats to include Q1, Q3, geometric mean and CV Table 7.2-1 - updated to make relevant protocol deviations (RPDs) applicable to the ST+LT period Tables 7.3.2.x – categories in table A updated in light of data, and table D added for Hematuria at the ST+LT treatment period

Date	Brief description of change
	Section 7.4.1 – clarification of how duplicate dosing data is handled at the ST+LT analysis
	Section 7.4.2 – sub-categories removed for allowed concomitant medication summary table
	Section 7.5.2 – the sensitivity analysis to be undertaken at the ST+LT treatment period were added
	Section 7.5.4 – confirmation that the proportion of subjects achieving a therapeutic glycaemic response is adjusted by baseline Hb1Ac
	Section 7.5.5 – clarification that no adjustments for multiplicity will be done - p-values are nominal only
	Section 7.5.9 – clarification of the author of the PRO report
	Section 7.5.5.2 – confirmation that model assumptions will be checked
	Section 7.5.5.3 – details of lipid summary added
	Section 7.5.5.4 and 8.2 – Updates in line with the errata to the ST CSR
	Section 7.5.8 – details of biomarker analysis added
	Section 7.6.1 – additional information about handling surgical or spontaneous amputations was added
	Section 7.6.3 – SAE listings added for ST+LT analysis
	Section 7.6.7, 8.3.1 and 8.5 – parameters were explicitly listed
	Section 7.6.5.1 – details were added to described how conflicting hypoglycaemia events were handled
	Section 7.6.5.5 – other AESI were defined more clearly
	Section 8.2 – handling of missing MRI data was added
	Table 8.4 – tables were updated and added to describe the various windows applied.

1 BACKGROUND AND RATIONALE

Type 2 diabetes mellitus (T2DM) is a chronic progressive disease, characterized by hyperglycemia and an increased risk of microvascular and macrovascular complications. Achieving and maintaining the glycemic treatment goal is challenging. Typically, the treatment paradigm consists of a step-wise addition of different classes of antihyperglycemic drugs, as most patients eventually require two or more agents to achieve or maintain glycemic targets. Among the medications approved for the treatment of T2DM, metformin is the recommended drug of choice for initiating oral therapy, while other classes of antidiabetic agents are typically added sequentially as second- and third-line agents. Despite multiple drugs and classes being available, many patients are still inadequately controlled. An ideal add-on to metformin would provide strong HbA1c reduction through complementary mechanisms of action (MoA), with weight loss, and no hypoglycemia.

Saxagliptin (BMS-477118) is a highly potent, selective, reversible, and competitive dipeptidyl peptidase 4 (DPP4) inhibitor. DPP4 is the enzyme responsible for the inactivation of glucagon-like peptide-1 (GLP-1) and glucose-dependent insulintropic polypeptide (GIP). By inhibiting DPP4, saxagliptin potentiates active endogenous GLP-1 concentrations, augmenting the physiological mechanism of insulin secretion and decreasing glucagon release, thereby reducing post-prandial and fasting glucose levels in patients with T2DM.

Dapagliflozin is a stable, competitive, reversible, highly selective, and orally active inhibitor of human renal sodium glucose co-transporter 2 (SGLT2), the major transporter responsible for renal glucose reabsorption in the kidney. Dapagliflozin's mechanism of action results in the direct and insulin-independent elimination of glucose by the kidney.

This is a Phase 3b study performed as part of the development program for saxagliptin / dapagliflozin fixed-dose combination (FDC, BMS-986098) to improve glycemic control as an adjunct to diet, exercise, and metformin treatment when treatment with both saxagliptin and dapagliflozin is appropriate. The study is intended to compare effects of saxagliptin co-administered with dapagliflozin in combination with metformin to glimepiride in combination with metformin. Saxagliptin and dapagliflozin have demonstrated, both individually and in combination with metformin, a favorable safety and tolerability profile. They have demonstrated a low propensity for hypoglycemia. Both drugs have either demonstrated weight neutrality (saxagliptin) or moderate weight reduction (dapagliflozin). Dapagliflozin and saxagliptin have also demonstrated persistent beneficial effects on HbA1c. Thus, a second-line oral dual add-on therapy with saxagliptin co-administered with dapagliflozin could be a new option, as part of a triple combination that includes drugs with complementary mechanisms of action, low risk of hypoglycemia, and the potential for moderate weight loss, providing a more effective and patient-friendly approach to the treatment of T2DM.

The purpose of this Study-specific Statistical Analysis Plan (SAP) is to present a detailed plan of the analyses of the Phase 3b study CV181-365.

Research Hypothesis:

Co-administration of saxagliptin and dapagliflozin, in addition to metformin, results in better glycemic control, as measured by HbA1c, over a treatment period of 52 weeks, compared to the addition of glimepiride to metformin in subjects with inadequately controlled T2DM.

Schedule of Analyses:

This analysis plan presents the objectives, endpoints, and analyses that will be conducted once all randomized subjects have either completed or been discontinued from the short-term double-blind period. All relevant queries must be resolved, and the database must be locked for this period before the blind is broken (for the sponsor) for analyses. Short-term plus long-term objectives, endpoints, and analyses performed at the time of the final database lock are also specified within this SAP.

2 STUDY DESCRIPTION

2.1 Study Design

The CV181-365 study is an international multicenter, randomized, double-blind, active-controlled, parallel-group Phase 3b study. The primary endpoint is the change from baseline in HbA1c with saxagliptin in combination with dapagliflozin on top of background therapy with metformin, compared to glimepiride. The primary endpoint of HbA1c will be assessed at 52 weeks, however, the trial will continue with a 104-week blinded extension. Subjects with documented T2DM treated with a stable dose of metformin will be enrolled. All subjects should be treated according to regional standards of care for diabetes. Subjects must be receiving metformin in accordance with the product label for their country. Approximately 440 subjects meeting all eligibility criteria will be randomized (1:1) to receive either saxagliptin co-administered with dapagliflozin or glimepiride. Enrollment of subjects based on disease state, and geographic region will be monitored and may be capped to ensure adequate representation. All potentially eligible subjects will undergo a screening visit. Each subject will sign an Informed Consent Form (ICF) prior to having any screening evaluations performed. Subjects who fulfill all eligibility requirements will enter a 2-week screening period and a 2-week lead-in period, during which they will continue their background medication with at least 1500 mg metformin. Approximately 2 weeks after entering the lead-in period, subjects will be expected to undergo a randomization visit. Subjects may withdraw prior to the randomization visit, or be withdrawn by study staff for any reason. At this visit, subjects will be re-evaluated by study staff to determine if after testing performed at the screening visit, after assessment of compliance, and any clinical changes that may have occurred during the lead-in period, the subject remains eligible and committed to participation in the study. If for any reason, prior to or during the randomization visit the subject is no longer eligible or interested in participating in the trial, he or she will be considered a lead-in failure, will not be randomized, and will not have additional follow up. If a subject is committed to participation, completes the lead-in period, and continues to meet eligibility criteria at the randomization visit, he or she will be randomized and will receive either saxagliptin 5 mg co-administered with dapagliflozin 10 mg plus metformin and matching placebo or glipimeride plus metformin and matching placebo in a double-blind fashion. Subjects will return to the site every 3 weeks to enable

titration of glimepiride from Week 3 up to Week 12, and then approximately every 12 to 13 weeks until the last visit (up to Week 156) for assessment of events related to the objectives of the study, tolerability and safety. Assessment of treatment compliance and provision of investigational product (IP) will be done at these visits.

Saxagliptin 5 mg tablets or matching placebo tablets will be provided, administered orally once daily for the 52-week double-blind treatment period and the 104-week subject and site blinded extension period. Saxagliptin 5 mg is the maximum recommend daily dose. No up- or down-titration of saxagliptin will be allowed. Dapagliflozin 10 mg tablets (also the maximum recommended daily dose) or matching placebo tablets will be provided, administered orally once daily for the 52-week double-blind treatment period and the 104-week subject and site blinded extension period. No up- or down-titration of dapagliflozin will be allowed.

[figure not shown]
Glimepiride 1-6 mg or matching placebo capsules, administered orally once daily, will be provided for the 156-week blinded treatment period. During the first 12 weeks, the glimepiride dose will be slowly titrated in a stepwise blinded fashion depending on glycemic control. For the duration of the study, FPG will be measured at the study center using a glucose analyzer provided by BMS. The investigator's decision on dose titration (either upwards if no issues with hypoglycemia or downwards if recurrent hypoglycemia occurs) will take both the plasma glucose measurements (measured prior to the visit), and the investigator's measurements at the titration visits, into account. The glimepiride dose will be titrated to optimal effect ($FPG \leq 110$ mg/dL [≤ 6.1 mmol/L]) or the highest tolerable dose during the first 12 weeks. The starting dose for glimepiride is 1 mg per day (once daily), which can be further increased by increments of 1-2 mg at 3-week intervals to a maximum of 6 mg per day (maximum recommended dose in the Summary of Product Characteristics and thus the maximum dose to be used in this study). The titration steps will be 2 mg, 3 mg, 4 mg, and 6 mg once daily if needed. In subjects for whom titration is not medically indicated at Week 3, re-assessment for titration will occur at Week 6, Week 9, and Week 12.

During the randomized treatment period, diet and life-style modification will continue to be reinforced. All randomized subjects who are rescued with insulin (or other oral anti-diabetes therapy) and taking randomized IP should continue scheduled study visits as planned in the Clinical Study Protocol (CSP). Subjects who decide to prematurely discontinue the investigational products will always be asked about the reason(s) and the presence of any AEs. Subject should return and complete the procedures described for End of Treatment Visit (EOT) as soon as possible but at the latest 7 days after discontinuation of investigational product. The subjects with unresolved AEs should also be followed-up if medically indicated as judged by investigator. All subjects who discontinue from treatment will follow the same visit schedule as subjects who remain on treatment. The only exception to this requirement is when a subject withdraws consent for all study procedures or loses the ability to consent freely (i.e., is imprisoned or involuntarily incarcerated for the treatment of either a psychiatric or physical illness). Subjects lost to follow-up (as defined by; unable to reach the subject after 3 documented phone calls, fax, email, or attempts to contact him/her through subject locator agencies [if allowed per national regulation])

and having sent one letter by registered/certified mail; all should be documented in the subject's medical records).

The study design schematic is presented in Figure 2.1-1.

Figure 2.1-1: Study Design Schematic

In addition, two exploratory sub-studies will be conducted along with the above main study.

The reduction in body weight consistently observed during treatment with dapagliflozin has been shown to result in total body fat reduction. A sub-study will investigate whether this reduction in body fat is equally distributed among subcutaneous and visceral adipose tissue or if there is a preferential loss of adipose tissue in the visceral compartment. Body composition measurements by magnetic resonance imaging (MRI) can separately quantify the subcutaneous and the visceral adipose tissue. Non-invasive quantification of liver lipid content by magnetic resonance imaging-estimated proton density fat fraction (MRI-PDFF) is an emerging biomarker for assessment of the beneficial effects of weight loss and improvement in glycemic control on liver lipid metabolism. In this protocol, a subpopulation of approximately 60 randomized subjects (~ 30 subject/treatment arm) who agree to participate (separate informed consent) will undergo MRI-PDFF measurement of subcutaneous and visceral adipose tissue, together with liver lipid content at baseline, at Week 52, and at Week 156.

Continuous Glucose Monitoring (CGM) is a useful technology (in addition to HbA1C) to qualitatively, as well as quantitatively, monitor the quality of glycemic control in the form of time spent in the euglycemic/hyperglycemic/hypoglycemic (blood glucose ≤ 70 mg/dL) ranges and the mean amplitude of glucose excursions (MAGE). Co-administration of saxagliptin and dapagliflozin is expected to better demonstrate less variability in glycemic control and more time spent in the euglycemic range compared to treatment with glimepiride administration. In this protocol, a subpopulation of approximately 120 randomized subjects (~ 60 subject/treatment arm) who agree to participate (separate informed consent) will have CGM performed for periods of 7 days at baseline and at Week 52 of treatment.

2.2 Treatment Assignment

CCI

Subjects entering the 52-week double-blinded short-term treatment period

Following completion of the lead-in period, subjects who meet the criteria will be randomly assigned by the IVRS at the Day 1 Randomization visit, to one of the following two (2) double-blind treatment arms in a 1:1 ratio:

- Blinded saxagliptin 5 mg and dapagliflozin 10 mg
- Titrated to blinded glimepiride 1 mg, 2 mg, 3 mg, 4 mg, or 6 mg

Randomization schedules for both subject treatment and containers will be generated and kept by BMS.

Subjects entering the 104-week long-term subject- and site-blinded treatment period

Following completion of the 52-week double-blinded treatment period, subjects eligible for the long-term subject- and site-blinded treatment period will be continued in their same randomization assignment based on their original randomization grouping. Subjects that were assigned to receive the blinded saxagliptin 5 mg and dapagliflozin 10 mg arm will continue to receive the blinded saxagliptin 5 mg and dapagliflozin 10 mg. Subjects that were assigned to receive the blinded glimepiride will continue to receive blinded glimepiride (at a dose of 1 mg, 2 mg, 3 mg, 4 mg, or 6 mg). At all study visits when study drug is dispensed, each subject will be assigned multiple container numbers by the IVRS. Container numbers will be assigned non-sequentially and will correspond to the numbers printed on the containers and bottles containing study drug, and will be recorded on the appropriate eCRF. The IVRS will be available 24 hours per day, 7 days a week.

2.3 Blinding and Unblinding

2.3.1 Blinding

The investigator, AstraZeneca personnel, and subjects will remain blinded to treatment allocation throughout the short-term, double-blind treatment period. The database used for the analysis of the short-term double-blind data of the study will be locked after all subjects have terminated the short-term double-blind treatment period of the study. The locked database will be unblinded for reporting purposes. To protect the integrity of the long-term treatment period of the studies, the subjects and investigators will not have access to the individual treatment assignments until the long-term treatment period has been completed.

For the duration of the double-blind treatment period (Day 1 to Week 52), the HbA1c and the urinary glucose values, including the urinary glucose:creatinine ratio, will be masked to the

sponsor and will not be available to the investigator. During the site- and subject-blinded treatment period, (after Week 52 and through Week 156), the above measurements will be unmasked to the sponsor. However, they still will not be available to the investigator except HbA1c values until after the study completion. HbA1c values will be provided to the investigator during the site- and subject-blinded treatment period.

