5.9 Results of Central Assessments

Blood and urine samples will be obtained at specified time points for laboratory evaluations (see [Appendix 2](#)). The central laboratory for this study will perform the analysis of all scheduled laboratory tests and will provide reference ranges for these tests. The central laboratory will provide specific instructions for collection, processing, packaging, and shipping of all samples.

During the Short Term double-blind treatment period (in non-rescued subjects), the HbA1c values will be blinded to the Investigator, subject, and to the Sponsor. These values will be provided to the Investigator after the study has been completed or after completion of the rescue visit in subjects who require the initiation of rescue medication. During the subject and site blinded long-term treatment period, after the Week 52 visit, the HbA1c values will not be blinded.

Spot urine samples were taken for glucose, albumin, creatinine, and determination of glucose:creatinine and albumin:creatinine ratios. Results for glucose and the glucose:creatinine ratio will be blinded to the Investigator and Sponsor throughout the study, (short-term treatment period and long-term treatment period). These values will be provided to the Investigator after the study has been completed. The albumin, creatinine, and albumin:creatinine ratio results will not be blinded during the study.

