6.3.5 Evaluable Subjects Data Set

The Evaluable Subjects Data Set will be a subset of the Randomized Subjects, with all data points collected after a relevant protocol deviation excluded from the data set. Relevant protocol deviations are defined as deviations that could potentially affect the interpretability of the study results. This is also known as the Per-protocol population. All decisions to exclude patients and/or data from the Randomized Subjects Data Set will be made prior to un-blinding the study and agreed by the study team.

The Evaluable Subject Data Set will only be used in the main efficacy result at Week 52 and no evaluable population will be summarized in the ST+LT CSR, although RPDs will be summarized for the ST+LT treatment period.

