7.6.6 Laboratory Evaluation

Unless otherwise specified, laboratory data (Glucagon, proinsulin, hematology and chemistry assessments, UACR, C-Reactive Protein (biomarker), N Terminal ProB Type Natriuretic Peptide

(biomarker) obtained after the start of study medication dosing up to and including 4 days (30 days for liver function laboratory tests) after the last short-term double-blind dosing date (or up to and including the start of the long-term treatment period, whichever comes first) will be considered as obtained during the short-term double-blind treatment period. Laboratory data obtained from the day after the last study medication + 4 days (30 days for liver function laboratory tests) up to the last visit date of the follow-up period will be considered as obtained during the follow-up period. Laboratory data obtained after the start of short-term treatment up to and including 4 days (30 days for liver function laboratory tests) after the last dose of short- or long-term medication will be considered as obtained during the combined short- and long-term treatment periods.

Listings for lab data will include everything in the database.

For liver safety, a summary of proportion of subjects with elevated liver test including elevated AT (ALT and/or AST) and total bilirubin (see Appendix 3 for definition) will be provided. In addition, a summary of proportion of subjects with elevated liver test and/or reported AE of hepatic disorder will also be provided.

Because the mechanism of action of dapagliflozin is known to impact urine glucose levels, urinalysis results of glucose will not be summarized. All laboratory evaluations performed by central laboratories will be included in summary tables. All laboratory tables for the CSRs will be produced in both conventional and SI units whenever available.

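### SAP 2.3.1 unmasks urinary glucose to the sponsor after Week 52, against protocol 5.9, and does not say that this waits for the short-term database lock

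*SAP*

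**What the plan says.** **SAP 2.3.1 (Blinding).** From Day 1 to Week 52, "the HbA1c and the urinary glucose values, including the urinary glucose:creatinine ratio, will be masked to the" sponsor. For the subject- and site-blinded period, after Week 52 and up to Week 156, "the above measurements will be unmasked to the sponsor". The investigator then receives HbA1c but not the urinary glucose results.

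**Protocol 5.9 (Results of Central Assessments).** On HbA1c the rule is the same: "after the Week 52 visit, the HbA1c values will not be blinded". On urinary glucose it differs: "Results for glucose and the glucose:creatinine ratio will be blinded to the Investigator and Sponsor throughout the study". The protocol names the short-term and the long-term period explicitly.

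**Order of lock and unblinding.** Under SAP 2.3.1 the short-term database is "locked after all subjects have terminated the short-term double-blind treatment period of the study". SAP Section 1 and protocol 8.4 also put the lock before the sponsor's unblinding.

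**Version and departures.** SAP 2.4 says that the plan follows Revised Protocol 04, with Amendment 05. Item 18 of that amendment clarified which laboratory results are blinded in which period. SAP Section 10, which tabulates departures from the protocol, does not mention urinary glucose masking.

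**The concern.** The two documents give opposite instructions for the same laboratory results, and these results carry information about the arm. SAP 7.6.6 leaves urinalysis glucose out of its summaries because "the mechanism of action of dapagliflozin is known to impact urine glucose levels". The introduction to the protocol describes glucosuria within an hour of dosing that persists through 104 weeks. Only one arm receives dapagliflozin.

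The SAP attaches unmasking to a treatment period that each subject enters on a personal date. If the sponsor saw long-term urinary glucose before the short-term lock, it could form a good idea of the arm for those subjects while two kinds of decision were still open:

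- Exclusions for the Evaluable Subjects Data Set (SAP 6.3.5): "All decisions to exclude patients and/or data from the Randomized Subjects Data Set will be made prior to un-blinding the study".
- The preferred-term lists for adverse events of special interest, which SAP 7.6.5 and 7.6.5.5 require to be settled before lock and unblinding.

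**Working it through.** The plan gives no figure to reproduce. The check is a comparison of text, followed by arithmetic on the visit schedule.

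**1. Sponsor access to each result**

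| Result | Period | Protocol 5.9 | SAP 2.3.1 |
|---|---|---|---|
| HbA1c | to Week 52 | blinded (non-rescued subjects) | masked |
| HbA1c | after Week 52 | not blinded | unmasked |
| Urinary glucose and ratio | to Week 52 | blinded | masked |
| Urinary glucose and ratio | after Week 52 | blinded | **unmasked** |

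Only the last row conflicts, and both instructions cannot be followed.

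**2. When long-term urine results could exist.** Protocol Table 5.1-3 schedules long-term spot urine at Week 117 and at the Week 156/Rescue/Discontinuation visit. Protocol 5.3.8.1 confirms that rescue and early-discontinuation visits after Week 52 use a kit that collects urine. HbA1c is assessed for rescue from Week 65. A discontinuation can occur at any time after Week 52.

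**3. Share of subjects past a given visit before the earliest possible lock.** The documents do not give the accrual period, so it is an assumption here. Let accrual be uniform over S weeks. The last subject reaches Week 52 at S + 52. A subject who entered at time t has passed Week L by then if t ≤ S + 52 − L. The share is therefore

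(S + 52 − L) / S, bounded by 0 and 1.

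- L = 65 (first scheduled HbA1c check for rescue): the share is (S − 13)/S, so accrual must exceed 13 weeks. S = 26 gives 13/26 = 0.50; S = 52 gives 39/52 = 0.75; S = 78 gives 65/78 = 0.83.
- L = 117 (first routine long-term spot urine): the share is (S − 65)/S, so accrual must exceed 65 weeks. S = 65 gives 0; S = 78 gives 13/78 = 0.17; S = 104 gives 39/104 = 0.38.

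The Week 65 shares are upper limits on exposure through rescue visits, because only a subject who is rescued gives such a sample. Discontinuation samples need no minimum beyond staggered entry, but again come only from those who discontinue. The time from the last Week 52 visit to the lock is ignored and would raise every share.

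**4. Earlier values.** The SAP does not say whether passing Week 52 would also release a subject's Day 1, Week 28 and Week 52 results. If it did, any staggered entry would create exposure before lock.

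**The case against.** The strongest reply is that the SAP sentence should be read in sequence. SAP 2.3.1 first keeps sponsor personnel blinded throughout the short-term period, then locks and unblinds, and only then describes the subject- and site-blinded period, whose name leaves out the sponsor. Read that way, unmasking follows lock and reveals nothing new about assignment. This reading is reasonable and would remove the early-unblinding risk. But the SAP does not state it, and the conflict with protocol 5.9 would remain.

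Other points that stand:

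- Protocol 9.1.1 requires the study to be run as the protocol describes. Nothing shows that the central laboratory released results on the SAP's wording.
- A reader might infer that a urinary glucose value identifies the arm almost with certainty. The documents give no distribution by arm. A discontinuation visit may also fall up to 7 days after the last dose (protocol 3.1), whereas SAP 8.3.1 accepts the ratio only up to one day after it. Strongly indicative is as far as the text goes.
- A reader might infer that the primary result is compromised. The primary analysis uses the Randomized Subjects Data Set, which is fixed by randomization and a first dose. The Evaluable set serves a sensitivity analysis, with largely objective deviation criteria listed in SAP Table 7.2-1. The special-interest summaries carry no formal test.
- Masking throughout the study, as protocol 5.9 has it, sits awkwardly with SAP 8.3.1, 8.5 and 12. These treat the spot urinary glucose:creatinine ratio as an efficacy measure to be summarized. The exclusion in SAP 7.6.6 covers urinalysis glucose only. Copying the protocol rule into the SAP would not settle the matter.
- SAP version 3 is dated 1 October 2019 and corrects discrepancies found while the short-term report was being prepared. A change of wording now cannot protect decisions taken before the short-term lock.

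**Conclusion.** The contradiction is certain. SAP 2.3.1 departs from the protocol version that it says it follows, and does not declare the departure. The SAP also omits the condition that would make the departure harmless, namely that unmasking waits for the short-term lock.

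The consequence is conditional. It requires unmasking subject by subject, and either a long-term urine result before lock or the release of earlier values at Week 52. How many subjects that would involve depends on the accrual period and on rescue and discontinuation rates, none of which the documents give. Any harm is confined to the time before lock, because the sponsor then learns the assignment directly. It would bear on the Evaluable-set exclusions and the special-interest term lists, and not on the primary analysis set.

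A reader might infer that the sponsor was in fact unblinded early. The documents do not show this. The Version 3 entry in the SAP's amendment history does not name Section 2.3.1, so it does not settle whether this wording was in force before the lock. The point should be corrected because the rule conflicts with its source and the correction is cheap.

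**What to change.** 1. In SAP 2.3.1, limit the post-Week 52 unmasking sentence to HbA1c.
2. State there that urinary glucose and the glucose:creatinine ratio stay masked to the sponsor at least until the short-term database has been locked and unblinded.
3. Reconcile this with protocol 5.9 and with the planned summary of the ratio in SAP 8.3.1, 8.5 and 12. List any remaining departure from the protocol in Section 10.
4. Record, from the central laboratory's release settings and the sponsor's access records, whether and when any urinary glucose result reached the sponsor before the short-term lock. If any did, report which subjects and which roles were involved, and whether the Evaluable-set exclusions and term lists had already been settled.

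The cost is a few sentences in the SAP, possibly one row in Section 10, and one check of access records. No new data or analyses are needed. Because version 3 postdates work on the short-term report, step 4 is the part that can still answer the question of substance.
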